6.2 DURATION OF STUDY PARTICIPATION

6.2.1 Duration of study participation for each patient

The patient will be considered in the study from informed consent signature until death consent withdrawal, or final OS cut-off date, whichever occurs first.

The duration of the study for a patient will include a period for screening of up to 21 days (or up to 28 days for FCBP). A cycle duration is 28 days. Patients will continue study treatment until disease progression, unacceptable AEs, patient wish, or any other reason. All adverse events occurring after informed consent signature will be reported up to 30 days after last study treatment administration.

After study treatment discontinuation, patients will return to the study site 30 days after the last dose of study treatments for end-of-treatment assessments, and 60 days after the last dose of study treatments for assessments including ADA (IPd arm only). If the ADA test at Day 60 is positive or inconclusive, ADA testing will be repeated every 30 days until negative (IPd arm only). If isatuximab is stopped prior to pomalidomide and dexamethasone, ADA will be tested on Day 1 of the 2 next cycles. If the ADA test at the second cycle administered without isatuximab is positive or inconclusive, ADA testing will be repeated every cycle until negative.

The related AEs and all SAEs regardless of relationship to study treatment ongoing at the time of study treatment discontinuation will be followed during the follow-up period until resolution or stabilization. During the follow-up period, any new related adverse events (regardless of seriousness) will be collected and followed until resolution or stabilization.

During FU, patients who discontinue study treatment due to progressive disease (PD) will be followed every 3 months (12 weeks) for further anti-myeloma therapy, second primary malignancies, and survival until death or final OS cut-off date, whichever comes first. Patients who discontinue the study treatment prior to documentation of PD will be followed-up monthly until confirmation of PD (even for patients who would initiate further anti-myeloma therapy without PD), and then every 3 months (12 weeks) for further anti-myeloma therapy, second primary malignancies, and survival, until death or final OS cut-off date, whichever comes first.

If a patient is still on treatment at the time of the cut-off date for OS and is benefitting from the study treatment, the patient can continue the study treatment until disease progression, unacceptable AEs, patient wish, or any other reason. For cycles completed after the cut-off date for OS, study treatment administration, pregnancy tests for FCBP, all related AEs, all serious AEs (regardless of relationship to study treatment), laboratory abnormalities if applicable, and reason of end of treatment (EOT) will continue to be collected. For patients in the IPd arm, 1 ADA sample should be drawn 60 ± 5 days after last study treatment administration. If ADA is positive or inconclusive at 60 days, the repeat samples will be taken every 30 ± 7 days until the results become negative (see [Section 1.3](#)). For patients still on treatment at the time of amended protocol 07, ADA sampling is no more required.

6.2.2 Determination of end of clinical trial (all patients)

PFS analysis (primary endpoint analysis) is event driven and the cut-off date for PFS analysis will be when 162 PFS events (progression or death, whichever comes first) have occurred (around 18 months from first patient being randomized).

The OS analysis is event driven and the final cut-off date will be when 220 deaths have occurred (around 51 months from first patient being randomized).

6.3 INTERIM ANALYSIS

No interim analysis of PFS is planned. An interim analysis of OS will be performed at time of the primary analysis of PFS and a second interim analysis will be performed when approximately 90% of OS events have occurred. The procedure and criteria for undertaking an interim analysis are described in [Section 11.5](#).

6.4 STUDY COMMITTEES

The **Steering Committee (SC)** will include a Chairman, investigators and Sponsor's representatives. The SC will be responsible for:

- Supervising the progress of the trial towards its overall objectives.
- Reviewing at regular intervals relevant information that may affect the study conduct.
- Discussing the implementation of the recommendations of the independent DMC.

An independent **Data Monitoring Committee (DMC)**, consisting of 5 external independent members (4 physicians with multiple myeloma expertise and 1 statistician), not associated with the conduct of the study or other study committees will meet regularly to as specified in the DMC charter:

- Review the progress of the trial.
- Review the safety data.
- Advise the Sponsor on potential modifications or communications that may be necessary to ensure the patient safety or protect the scientific integrity of the trial. The Sponsor will make the final decision(s).

The first meeting will be set up to review early safety results (eg, after approximately 30 patients have completed at least 2 cycles), and then periodically. Ad-hoc DMC meetings may also be held if a significant safety issue or issue deemed important for discussion arise on this or any other studies of isatuximab. After each meeting, the DMC will advise the SC and the Sponsor's representatives regarding the continued safety of treating ongoing and future study patients, as well as the course of action regarding the conduct of the trial.

The DMC procedures will be detailed in the DMC charter and approved by the DMC members. The charter will be finalized before the first patient enrolled.

An **Independent Response Committee (IRC)** will determine disease response and progression according to efficacy MM laboratory data (central laboratory results), bone marrow, and imaging as per IMWG criteria and in line with the IRC charter up to primary analysis on PFS; no IRC review will be performed after the cut-off for the primary analysis.

7 SELECTION OF PATIENTS

7.1 INCLUSION CRITERIA

Eligible patients will be considered for inclusion in this study if they meet all of the following criteria (all necessary baseline studies for determining eligibility must be obtained within 21 days prior to randomization [or 28 days for FCBP]):

- I 01. Age ≥ 18 years or country's legal age of majority if the legal age is >18 years old.
- I 02. Patients must have a documented diagnosis of multiple myeloma with evidence of measurable disease.
 - Serum M protein ≥ 0.5 g/dL measured using serum protein immunoelectrophoresis and/or,
 - Urine M protein ≥ 200 mg/24 hours measured using urine protein immunoelectrophoresis.
- I 03. Patients must have received at least 2 prior lines of anti-myeloma therapy, which must include at least 2 consecutive cycles of lenalidomide and a proteasome inhibitor (bortezomib, carfilzomib or ixazomib) given alone or in combination.

Note: An induction treatment followed by ASCT and consolidation/maintenance is considered as one line of treatment.

- I 04. Patients must have failed treatment with lenalidomide and a proteasome inhibitor (bortezomib, carfilzomib or ixazomib) alone or in combination, defined by any of the following (failure to lenalidomide and a proteasome inhibitor can have occurred at any line of therapy):
 - Progression has occurred while on or within 60 days from end of the treatment with lenalidomide and/or a proteasome inhibitor.
 - In case of previous response \geq PR to lenalidomide and/or a proteasome inhibitor, patient must have progressed within 6 months after discontinuation of the treatment.
 - Patients who have developed intolerable toxicity after a minimum of 2 consecutive cycles of a regimen containing lenalidomide and a proteasome inhibitor (bortezomib, carfilzomib or ixazomib) alone or in combination. Intolerance is defined as below:
 - For proteasome inhibitor containing regimens: any toxicity leading to discontinuation of a proteasome inhibitor, like \geq G2 peripheral neuropathy or \geq G2 neuropathic pain. Peripheral neuropathy must be \leq G1 before study entry (according to National Cancer Institute Common Terminology for Adverse Event (NCI-CTCAE v4.03),

- For lenalidomide containing regimens: any toxicity leading to discontinuation of lenalidomide, like G3 rash. Rash must not have been G4 and other non-hematologic toxicities should not have been G4. All non-hematologic toxicities must be \leq G1 before study entry.

I 05. Patients must have progressed on or within 60 days after end of the previous therapy before study entry, ie, refractory to the last line of treatment. This patient population includes the following two categories:

- Refractory disease: patients who were refractory to all previous lines of treatment but should have achieved at least a MR in one previous line.
- Relapsed and refractory disease: patients who were relapsed from at least one previous line of treatment and refractory to the last line of treatment. Patients can be refractory to other previous line/lines of treatment.

Note: Patients must have achieved a MR or better to at least one of the previous lines of treatment (ie, primary refractory disease is not eligible).

I 06. Patient has given voluntary written informed consent before performance of any study related procedures not part of normal medical care, with the understanding that consent may be withdrawn by the patient at any time without prejudice to his/her medical care.

7.2 EXCLUSION CRITERIA

Patients who have met all the inclusion criteria listed in [Section 7.1](#) will be screened for the following exclusion criteria.

- E 01. Primary refractory multiple myeloma defined as: patients who have never achieved at least a MR with any treatment during the disease course.
- E 02. Free Light Chain measurable disease only.
- E 03. Patient with prior anti-CD38 monoclonal antibody treatment with progression on or within 60 days after end of anti-CD38 monoclonal antibody treatment or failure to achieve at least MR to treatment (ie, refractory to anti-CD38).
- E 04. Prior therapy with pomalidomide.
- E 05. Any anti-myeloma drug treatment within 14 days before randomization, including dexamethasone.
- E 06. Prior allogenic HSC transplant with active graft versus host disease (GvHD) (GvHD any grade and/or being under immunosuppressive treatment within the last 2 months).
- E 07. Any major procedure within 14 days before the initiation of the study treatment: plasmapheresis, major surgery (kyphoplasty is not considered a major procedure), radiotherapy.

- E 08. Patient who has received any other investigational drugs or prohibited therapy for this study within 28 days or 5 half-lives from randomization, whichever is longer.
- E 09. ECOG status >2 ([Appendix B](#)).
- E 10. Platelets <75 000 cells/ μ L if <50% of bone marrow (BM) nucleated cells are plasma cells and, <30 000 cells/ μ L if \geq 50% of BM nucleated cells are plasma cells. Platelet transfusion is not allowed within three days before the screening hematological test.
- E 11. ANC <1000 μ L (1×10^9 /L). The use of G-CSF is not allowed to reach this level.
- E 12. Creatinine clearance <30 mL/min (MDRD Formula, see [Appendix A](#)).
- E 13. Total bilirubin >2 x ULN.
- E 14. Corrected serum calcium >14 mg/dL (>3.5 mmol/L).
- E 15. AST and/or ALT >3 x ULN.
- E 16. Ongoing toxicity (excluding alopecia and those listed in eligibility criteria) from any prior anti-myeloma therapy >G1 (NCI-CTCAE v4.03).
- E 17. Hypersensitivity to IMiDs (thalidomide or lenalidomide) defined as any hypersensitivity reaction leading to stop IMiDs within the 2 first cycles or reaction, which does meet intolerance definition (see [I 04](#)).
- E 18. Hypersensitivity to dexamethasone, sucrose histidine (as base and hydrochloride salt) and polysorbate 80 or any of the components of study therapy that are not amenable to premedication with steroids, or H2 blockers that would prohibit further treatment with these agents.
- E 19. Significant cardiac dysfunction; myocardial infarction within 12 months; unstable, poorly controlled angina pectoris.
- E 20. Diagnosed or treated for another malignancy within 3 years prior to randomization with the exception of complete resection of basal cell carcinoma or squamous cell carcinoma of the skin, an in situ malignancy, or low risk prostate cancer after curative therapy.
- E 21. Known to be HIV+ or to have hepatitis A, B or C active infection.
- E 22. Malabsorption syndrome or any condition that can significantly impact the absorption of pomalidomide.
- E 23. Active primary amyloid-light (AL) amyloidosis (evidence of end organ damage or receiving treatment for amyloidosis).
- E 24. Concomitant plasma cell leukemia.

- E 25. Unable or unwilling to undergo to thromboprophylaxis.
- E 26. Daily requirement for corticosteroids (equivalent to ≥ 10 mg/day of prednisone) for more than 7 days (except for inhalation corticosteroids).
- E 27. Pregnant or breastfeeding female or female who intends to become pregnant during the participation in the study. Females of childbearing potential (FCBP) unwilling to prevent pregnancy by the use of 2 reliable methods of contraception for ≥ 4 weeks before the start of study treatment, during treatment (including dose interruptions), and up to 3 or 5 months following the last dose of study treatment for Pd and IPd respectively, and/or who are unwilling or unable to be tested for pregnancy before study treatment initiation (2 negative tests), weekly during 1st month of treatment and then prior each treatment cycle administration or every 2 weeks in case of irregular menstrual cycles up to 3 or 5 months following the last dose of study treatment for Pd and IPd respectively.
- E 28. Male participants who disagree to practice true abstinence or disagree to use a condom during sexual contact with a pregnant female or a FCBP while participating in the study, during dose interruptions and at least 3 or 5 months following study treatment discontinuation for Pd and IPd respectively, even if has undergone a successful vasectomy.

Note 1: a FCBP is a female who: 1) has achieved menarche at some time point, 2) has not undergone a hysterectomy or bilateral oophorectomy or 3) has not been naturally postmenopausal (amenorrhea following cancer therapy does not rule out childbearing potential) for at least 24 consecutive months (ie, has had menses at any time in the preceding 24 consecutive months).

Note 2: True abstinence is acceptable when this is in line with the preferred and usual lifestyle of the patient. Periodic abstinence (eg, calendar, ovulation, symptothermal, post-ovulation methods) and withdrawal are not acceptable methods of contraception.

- E 29. All patients who disagree to refrain from donating blood while on study treatment and for 4 weeks after discontinuation from this study treatment.
- E 30. All patients who do not agree to keep study treatment for their personal use only.
- E 31. Any country-related specific regulation that would prevent the patient from entering the study.
- E 32. Any severe acute or chronic medical condition which could impair the ability of the patient to participate in the study or interfere with interpretation of study results (eg, systemic infection unless specific anti-infective therapy is employed) or patient unable to comply with the study procedures.

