 - Patients still receiving isatuximab at the time of amended protocol 07 will switch to the registered infusion rate as described below. For these patients, premedication for the prevention of IAR has to be given for the first 4 isatuximab infusions. Patients who do not experience an IAR upon 4 consecutive administrations of isatuximab may have their need for subsequent premedication reconsidered, at the Investigator's discretion.
 - First isatuximab infusion: initiate infusion at 25 mL/hour. In the absence of IARs after 1 hour of infusion, increase infusion rate by 25 mL/hour increments every 30 minutes, to a maximum of 150 mL/hour. In case of Grade 2 IAR during first infusion, infusion could be restarted at one-half of the initial infusion rate (12.5 mL/hour) when the IAR improves to Grade ≤ 1 . If symptoms do not recur after 30 minutes of infusion, the infusion rate may be increased by 25mL/hour increments every 30 minutes, until the total volume is infused to a maximum rate of 150mL/hour.
 - Second infusion: Initiate infusion at 50 mL/hour. In the absence of Grade 2 IAR after 30 minutes of infusion, increase rate to 100 mL/hour for 30 minutes, then, to 200 mL/hour until the total volume is infused. In case of Grade 2 IAR during second

infusion, infusion could be restarted at one-half of the initial infusion rate (25 mL/hour) when the IAR improves to Grade ≤ 1 . If symptoms do not recur after 30 minutes, the infusion rate may be increased by 50 mL/hour increments every 30 minutes, until the total volume is infused to maximum rate of 200 mL/hour,

- Third and subsequent infusions: Initiate infusion at a fixed infusion rate of 200 mL/hour, until the total volume is infused. In case of Grade 2 IAR during third infusion, infusion could be restarted at one-half (100 mL/hour) of the infusion rate (100 mL/hour) when the IAR improves to Grade ≤ 1 . If symptoms do not recur after 30 minutes, the infusion rate may be increased by 50 mL/hour increments every 30 minutes, until the total volume is infused to maximum rate 200 mL/hour.
- Guidelines for patients who develop IARs are provided in [Section 10.6.1](#).

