- Females of childbearing potential with regular or no menstrual cycles must agree to have pregnancy tests weekly for the first 28 days of pomalidomide treatment, including dose interruptions and then every 28 days throughout the remaining duration of pomalidomide treatment, including dose interruptions, at pomalidomide discontinuation, and monthly up to 3 or 5 months following study treatment discontinuation for Pd and IPd respectively. If menstrual cycles are irregular, the pregnancy testing must occur weekly for the first 28 days of pomalidomide treatment, including dose interruptions, and then every 14 days throughout the remaining duration of pomalidomide treatment, including dose interruptions, at pomalidomide discontinuation, and at Days 14 and monthly up to 3 or 5 months following study treatment discontinuation for Pd and IPd respectively.
- At each visit, the Investigator must confirm with the FCBP that she is continuing to use two reliable methods of birth control at each visit during the time that birth control is required.
- If pregnancy or a positive pregnancy test does occur in a study patient, pomalidomide must be immediately discontinued.
- Pregnancy testing and counseling must be performed if a patient misses her period or if her pregnancy test or her menstrual bleeding is abnormal. Pomalidomide treatment must be temporarily discontinued during this evaluation.
- Females must agree to abstain from breastfeeding during study participation and for at least 3 or 5 months after study treatment discontinuation for Pd and IPd respectively.

Male Patients:

- Must practice complete abstinence or use a condom during sexual contact with pregnant females or FCBP throughout the entire duration of pomalidomide treatment, during dose interruptions and for at least 3 or 5 months following study treatment discontinuation for Pd and IPd respectively, even if he has undergone a successful vasectomy.
- If pregnancy or a positive pregnancy test does occur in the partner of a male study patient during study participation, the investigator must be notified immediately.
- Male patients should not donate semen or sperm during therapy or for at least 3 or 5 months following discontinuation of study treatment for Pd and IPd respectively.

Additional precautions

- Female caregivers of childbearing potential should not touch the pomalidomide capsules or bottles unless they are wearing gloves.

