- Patients should be instructed never to give pomalidomide to another person.
- Patients should not donate blood during therapy and for at least 3 or 5 months following discontinuation of study treatment for Pd and IPd respectively.

- Only enough pomalidomide for one cycle of therapy may be prescribed with each cycle of therapy.
- Any unused pomalidomide must be returned as instructed in the Pomalidomide Pregnancy Prevention Plan ([Appendix L](#)) or the country specific risk management plan in countries where pomalidomide is not supplied by the Sponsor.

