11.1 DETERMINATION OF SAMPLE SIZE

The sample size calculation is based on the primary efficacy endpoint (ie, PFS). The following assumptions were used:

- PFS has an exponential distribution in both treatment groups.
- Pd arm has a median PFS of 4.0 months.
- IPd arm will have 40% risk reduction in hazard rate in comparison to Pd arm. The targeted hazard ratio is 0.60, which corresponds to an improvement in the true median progression free survival time from 4 months to 6.67 months.
- A log-rank test at a one-sided 2.5% significance level.

Based on the above assumptions, a total of 162 PFS events are needed to achieve a 90% power for the study.

Objective for OS also support the sample size calculation using the following assumptions:

- OS has an exponential distribution in both treatment groups.
- Pd arm has a median OS of 13.0 months.
- IPd will have 31.5% risk reduction in hazard rate in comparison to Pd arm. The targeted hazard ratio is 0.685 and this is expected to correspond to a difference of 6 months in median OS between the control arm and the experimental arm.
- A log-rank test at a one-sided 2.5% significance level.
- An interim analysis for efficacy assessment on OS is planned at the time of primary analysis on PFS which is estimated to occur when about 36% of the OS events will be observed and a second interim analysis is planned when approximately 90% of the OS events have occurred. An O'Brien and Fleming α -spending function will be used to obtain the nominal significance levels for the interim and final analyses of survival (see [Section 11.5](#)).

Based on the above assumptions, a total of 220 deaths are needed to achieve 79.3% power for the study.

A maximum of 300 patients (150 in each arm) would be adequate to achieve the targeted number of events for both PFS and OS. After the PFS analysis, no more patients will be randomized and OS analysis will be performed on the number of patient already randomized.

Assuming a uniform accrual rate of 15 patients per month, cut-off dates for primary analyses of PFS and final OS analysis will be approximately 18 and 51 months after first patient in (FPI) respectively.

PFS, ORR and OS will be tested according to a closed test procedure according this order. Please refer to [Section 11.4.2.3](#) for further details on the closed test procedure.

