15 CLINICAL TRIAL PROTOCOL AMENDMENTS

All appendices attached hereto and referred to herein are made part of this clinical trial protocol.

The Investigator should not implement any deviation from, or changes to the clinical trial protocol without agreement by the Sponsor and prior review and documented approval/favorable opinion from the IRB/IEC and/or notification/approval of health authorities (competent regulatory authority) of an amendment, as required by local regulation, except where necessary to eliminate an immediate hazard(s) to clinical trial patients, or when the change(s) involves only logistical or administrative aspects of the trial. Any change agreed upon will be recorded in writing, the written amendment will be signed by the Investigator and by the Sponsor and the signed amendment will be filed with this clinical trial protocol.

Any amendment to the clinical trial protocol requires written approval/favorable opinion by the IRB/IEC prior to its implementation, unless there are overriding safety reasons.

In case of substantial amendment to the clinical trial protocol, approval from the health authorities (competent regulatory authority) will be sought before implementation.

In some instances, an amendment may require a change to the ICF. The Investigator must receive an IRB/IEC approval/favorable opinion concerning the revised ICF prior to implementation of the change and patient signature should be re-collected if necessary.

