**Table 1 - Statistical analysis plan statistical changes**

SAP version number	Date approved	Rationale	Description of statistical changes
3	20-Oct-2020	An amendment (Amendment 6) to the protocol was issued after the primary analysis to add a second interim analysis for OS. The current version of SAP is consistent with this protocol amendment.	An interim analysis has been added at approximately 90% of events. The boundaries for final analysis were updated.
3	20-Oct-2020	To further evaluate the impact of study treatments on subsequent therapies	The following analyses have been added: 
 
- Analysis of PFS2 as per investigator
 
- Summary of further anti-myeloma treatments by drug class and by number of lines
 

SAP version number	Date approved	Rationale	Description of statistical changes
			
 
- ORR, VGPR rate and CR rate on subsequent therapy by number of subsequent line and selected drug class or agent
 
- PFS on first line of further therapy (based on investigator assessment)
 

3	20-Oct-2020	One analysis was added to better characterize the cytogenetic profile of patients	Summary of gain(1q21) abnormality at baseline
3	20-Oct-2020	Clarification	Definition of R-ISS stage was clarified
3	20-Oct-2020	One analysis was added to identify the TEAEs related to COVID19	Summary of COVID19 related TEAEs
3	20-Oct-2020	Some analyses were planned only for the primary analysis or will not be provided at time of second interim and final OS analyses because not deemed relevant at this stage of the study	A table describing analyses that will be provided at time of primary analysis of PFS and second interim and final OS analyses has been added in section 3.
2	07-Nov-2018	Safety analyses were added to better characterize the safety profile and to account for FDA comments on the submission strategy	
The following analyses have been added:
 
 
- Cumulative exposure to treatment in patient-years
 
- Isatuximab dose reductions
 
- Infusions without IR medication
 
- Exposure-adjusted analyses of TEAEs
 
- Indirect antiglobulin test
 
- Neutropenic complications
 
- Thrombocytopenia and haemorrhages
 
- Hemolytic disorders
 
- Autoimmune disorders
 

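### E 29 accepts a 4-week pause in blood donation after study treatment, while section 8.9.4 requires at least 3 months (Pd) or 5 months (IPd)

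*Protocol*

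**What the plan says.** E 29 reads the same in the Clinical Trial Summary and in Protocol section 7.2. It excludes "All patients who disagree to refrain from donating blood while on study treatment and for 4 weeks after discontinuation from this study treatment".

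Protocol section 8.9.4, under additional precautions, sets the conduct rule: "Patients should not donate blood during therapy and for at least 3 or 5 months following discontinuation of study treatment for Pd and IPd respectively".

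Two neighbouring rules carry the longer period. E 28, on male contraception, applies "during dose interruptions and at least 3 or 5 months following study treatment discontinuation for Pd and IPd respectively". The semen rule in 8.9.4 reads "Male patients should not donate semen or sperm during therapy or for at least 3 or 5 months following discontinuation of study treatment".

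Appendix L, the pomalidomide pregnancy prevention plan, contains a third figure. Its section 2.5.3 asks patients not to give blood until at least 28 days after the last pomalidomide dose. The counselling documents in its sections 3.1, 3.2 and 4 repeat this for women of childbearing potential, other women and men. A trained counsellor must complete and sign the relevant document before each dispensing. Section 8.9.4 requires all participants to follow Appendix L, or the country plan where the sponsor does not supply pomalidomide.

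**The concern.** An eligibility criterion about willingness exists to secure agreement to a rule that will bind the patient later. Here the criterion asks for less than the rule, so a patient can meet E 29 in full and still not have agreed to what 8.9.4 requires. Nothing in the protocol says which period governs.

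The rule protects third parties, the recipients of donated blood. Site staff could take the shorter period from E 29. For patients still on treatment, the likelier source is the Appendix L counselling document, because it is used again at every dispensing.

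**Working it through.** **Side by side (current text only)**

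| Source | Starts at | Pd | IPd |
|---|---|---|---|
| E 29 (Summary and 7.2) | discontinuation of study treatment | 4 weeks | 4 weeks |
| 8.9.4, additional precautions | discontinuation of study treatment | at least 3 months | at least 5 months |
| Appendix L, 2.5.3, 3.1, 3.2 and 4 | last dose of pomalidomide | at least 28 days | at least 28 days |

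The first two rows concern the same act, patients and starting point, so they are directly comparable. The third counts from a different event and concerns one drug.

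**Size of the mismatch.** Assumption: a month is 30 to 30.44 days. Four weeks = 4 × 7 = 28 days.

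- Pd: 3 × 30 = 90 and 3 × 30.44 = 91.3 days. Shortfall 90 − 28 = 62 to 91.3 − 28 = 63.3 days. Ratio 90/28 = 3.2 to 91.3/28 = 3.3.
- IPd: 5 × 30 = 150 and 5 × 30.44 = 152.2 days. Shortfall 150 − 28 = 122 to 152.2 − 28 = 124.2 days. Ratio 150/28 = 5.36 to 152.2/28 = 5.44, about 5.4.

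**Does Appendix L reconcile the texts?** No. It is a minimum, so 8.9.4 can exceed it without contradiction. E 29 has no such qualifier and counts from the end of study treatment, which section 8.2.1 defines as including isatuximab in the IPd arm. Appendix L also gives 28 days for contraception and semen donation, yet E 27 and E 28 follow the 3 or 5 months of 8.9.4. E 29 alone of the three stays at the pomalidomide figure.

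**Does E 32 reconcile them?** No. It excludes patients unable to comply with study procedures but states no donation period.

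**Was the longer window intended?** The amendment history in Appendix P is used here as context only. Its amendment 05 entry names blood donation among the 8.9.4 items set at 3 or 5 months. The reason given is a re-estimated isatuximab half-life of 28 days, with contraception to last five half-lives: 5 × 28 = 140 days, or 140/30.44 = 4.6 months. Four weeks is one half-life. That reasoning supports the IPd figure. The documents give no separate rationale for 3 months in Pd, but 8.9.4 states it as the trial's rule.

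**Who is still affected?** Protocol 11.1 says "After the PFS analysis, no more patients will be randomized", and SAP Table 1 records that amendment 6 was "issued after the primary analysis to add a second interim analysis for OS". The current protocol is amendment 07, so enrolment appears closed. Section 8.2.1 nevertheless provides for some patients: "Patients still receiving isatuximab at the time of amended protocol 07 will switch to the registered infusion rate". Their number is not given, and their post-treatment window is still ahead. Section 10.1.7 also lets patients continue after the final OS cut-off. Once they stop, only follow-up of ongoing SAEs and of related AEs is collected, so the instruction has to be given before treatment ends.

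**The case against.** The best defence is that no instruction conflicts in practice. A patient who waits 3 or 5 months also satisfies 4 weeks and at least 28 days. E 29 sets willingness at entry, 8.9.4 sets conduct, and editing E 29 now changes nobody's eligibility. All of this is right, and it limits the weight of the point. It does not make the two periods agree.

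A second defence is that 4 weeks is not a stray figure. It matches Appendix L, which section 15 makes part of the protocol. For Pd patients, who receive no isatuximab, the half-life reasoning does not apply. This also stands in part: the direction of the error is better documented for IPd than for Pd. For Pd the case rests on 8.9.4 stating 3 months as the rule and on E 27 and E 28 following it.

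The match with Appendix L also shows that editing E 29 alone would leave the shorter figure in the counselling documents signed before each dispensing. The correction has to cover that route too.

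A reader might infer that patients were told the wrong period, or that recipients were put at risk. The documents do not support this. The consent form is not among them, 8.9.4 already governs conduct, and the day counts measure a difference in wording, not a hazard.

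**Conclusion.** The mismatch is real in current text and minor. E 29 accepts 28 days where 8.9.4 requires roughly 90 days (Pd) or 150 days (IPd) from the same point, and neither Appendix L nor E 32 resolves it. The day counts depend only on the month convention.

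No endpoint, sample size, error rate or analysis is touched. That enrolment is closed is an inference from protocol 11.1 and SAP Table 1, not a direct statement. Remaining exposure is confined to patients still on treatment. Section 8.2.1 documents such patients for isatuximab recipients; the number in either arm is unknown.

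A reader might also conclude that 3 months is pharmacologically necessary for Pd, or that Appendix L is wrong. Neither follows: no Pd rationale is given, and Appendix L is a valid minimum for pomalidomide.

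**What to change.** At the next amendment needed for another reason:

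1. In the Clinical Trial Summary and section 7.2, change the E 29 period to at least 3 months (Pd) or 5 months (IPd) after discontinuation of study treatment.
2. Add one sentence to 8.9.4: its blood-donation window prevails over the 28-day minimum in Appendix L and must be given to patients at the counselling before each pomalidomide dispensing.

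Until then, remind patients still on treatment of the 8.9.4 window. This restates an existing rule and needs no protocol change.

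The cost is two edited lines, one added sentence and a short reminder, with no new visits, samples, data or analyses. A separate amendment is not justified. Section 15 states: "Any amendment to the clinical trial protocol requires written approval/favorable opinion by the IRB/IEC prior to its implementation". It adds that a revised consent form may be needed in some instances. The planned number of sites is about 140 (SAP 1.1) to 150 (Clinical Trial Summary), so bundling the change avoids an extra approval round across them.
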